## 1.0 Objectives / Specific Aims

The specific aims of this protocol are to:

**Aim 1.** (Months 03-12). To theater test and deliver the un-adapted CPT protocol and one session adherence intervention (Lifesteps) with 12 trauma-exposed PLWH presenting for HIV treatment at the MUSC Ryan White Clinic and collect qualitative feedback for modifications to ensure feasible administration and relevant incorporation of HIV-related messages and/or content specific to HIV-related PTSD. Specific activities are to:

- A. Test methods and measurement protocol of the beta version of the research protocol.
- B. Utilize feedback provided through exit interviews, topical experts, and advisory panel discussion to shape any refinement of the integrated CPT and one session adherence protocol.
- C. Incorporate qualitative feedback into the CPT-L manual.

**Aim 2.** (Months 13-30). To assess feasibility of the modified CPT protocol (CPT-L) compared to Lifesteps in 60 PLWH with comorbid PTSD over 3 months (baseline, post intervention, 3 month follow-up) in a pilot RCT to assess key variables for subsequent efficacy testing (attendance, ART adherence, HIV symptom distress, CD4 count, viral load, PTSD symptoms, avoidant coping). Specific feasibility benchmarks are:

- A. Achieve a recruitment rate of 4+ patients per month and retention rate of 80% or higher.
- B. Obtain variability estimates of outcomes (less than 10% missing data) and initial indicators of treatment effects for the following hypotheses in the subsequent efficacy trial:
  - a. Participants who receive the CPT-L protocol will have improved HIV symptom distress, ART adherence, clinic attendance, and viral load at post intervention and 3-month follow up vs. control.
  - b. Participants who receive the CPT-L protocol will report lower PTSD at post intervention and 3-month follow up versus those in the Lifesteps Control.
- C. Assess qualitative feedback from exit interviews for high satisfaction, successful saturation of themes, and action plan development, in conjunction with Advisory Board, to refine the intervention for an R01.

**Exploratory Aims.** 1) We will assess between-group differences in other problems that commonly occur among PLWH and PTSD (substance misuse, depression). 2) Avoidant coping will be examined as a potential mechanism of action for the relationship between CPT-L and improved adherence.

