## 4.0 Study Endpoints

Study end points for both Aims I and II include: successful study completion, participant consent withdrawal, and PI termination due to failure to adhere to the protocol, loss of contact with the participant, and/or unexpected adverse events.

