## 12.0 Data Management

### Sample size, Statistical Power and Analysis

Sample size justification. As the study is designed to demonstrate feasibility, sample size was determined based on pragmatic considerations, rather than formal power analysis. The study plans to enroll 60 PLWH randomized to CPT-L or Lifesteps. This sample size is adequate to assess feasibility outcomes (enrollment, attrition, retention, adherence to protocol and fidelity). The sample size recruited during our recruitment period (18 months) will allow the team to specifically justify that we can approach a reasonable sample for a larger RCT in an expanded recruitment period. Further, with a target retention rate of ≥90%, an enrolled sample of 60 participants produces a 95% confidence interval from 82% to 98% and an adherence rate of 80% will produce a 95% confidence interval between 70% and 90%. The study will produce both within and between treatment group estimates of visit attendance (yes/no), ART adherence (85% of doses taken), and proportion of detectable viral load (yes/no). Further, if mean HIV Symptom Severity, CD4 cell counts, PCL and CAPS-5 scores will be assessed post-intervention and a sample of 30 participants in each group will provide adequate power to determine estimated a confidence interval with a difference of ½ a standard deviation (0.51 SD) of the between group mean estimate. If the difference in proportion of participants with detectable viral load is 10% in the CPT group and 20% in the SOC Lifesteps group at the close of treatment (10% difference), the sample of 30 participants in each study group will provide an 18% confidence interval on either side of the estimated difference.

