
Data Analysis Aim 2. Descriptive analyses will characterize the entire sample and two conditions as appropriate using measures of central tendency or frequency distributions and proportions. Feasibility will be determined by patient willingness to be screened, proportion of participants meeting PTSD criteria, and flow of participants through the study. Feasibility of assessments will be examined through self-report and medical record abstraction. While CPT has been evaluated in other populations, acceptability within PLWH is important for feasibility data. Intervention feasibility will be monitored through randomization, session attendance and quality assurance data collection on intervention fidelity and supervision. Exit interviews will be analyzed using the same techniques for qualitative analyses described for Aim 1. Study feasibility will be determined by ability to adequately randomize and retain study participants throughout study intervention and follow-up, determined through ability to successfully randomize 4+ patients per month and retain 90% of randomized patients throughout the study. In addition to retention, a low rate of missing primary outcome data ( $\leq 10\%$  missing) will demonstrate ability to integrate the intervention with standard clinical care components and medical health records. Protocol adherence will be monitored weekly and reported as the proportion of weekly PCL checklists completed, and distribution of clinician rated treatment engagement and cooperation levels. Acceptable protocol adherence will be determined by completion of  $\geq 80\%$  of assigned weekly PCL checklists across participants.

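### The pilot's feasibility rules conflict on retention (80% or 90%) and on missing data (below 10% or at most 10%), and the missing-data rule refers to a primary outcome that is never named

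*Combined protocol and SAP*

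**What the plan says.** Section 1.0 (Objectives / Specific Aims), Aim 2, gives two of its benchmarks as "Achieve a recruitment rate of 4+ patients per month and retention rate of 80% or higher" and "Obtain variability estimates of outcomes (less than 10% missing data". The second applies to outcomes in general. The aim lists seven key variables without ranking them.

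Section 12.0 restates the rules differently. The sample size paragraph says "The study plans to enroll 60 PLWH randomized to CPT-L or Lifesteps", sets a retention target of at least 90%, and reports that "an enrolled sample of 60 participants produces a 95% confidence interval from 82% to 98" per cent. Data Analysis Aim 2 requires the study to "retain 90% of randomized patients throughout the study" and adds "a low rate of missing primary outcome data", with a ceiling of 10% inclusive.

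Section 4.0, where a primary outcome might be expected, lists only ways in which participation ends: "Study end points for both Aims I and II include: successful study completion, participant consent withdrawal", followed by forms of termination by the PI. The analysis text in section 12.0 labels some measures exploratory or secondary, but none primary.

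Section 10.0 plans to assess every participant at every timepoint, including those who stop treatment. Section 10.0 and Table 2 take viral load, CD4 count and appointment attendance from the medical record, whereas CAPS-5 and the self-report scales need contact with the participant.

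**The concern.** These are the rules by which the pilot will be declared feasible or not, and so will support or fail to support the later efficacy trial. A decision rule should give one answer for one dataset, and these do not. Two retention thresholds and two missing-data cut-offs are in force at once. One missing-data rule also points to an outcome that no section identifies, at an unstated visit, over an unstated denominator.

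Outcomes from interview, questionnaire and clinic record can go missing for different reasons. If the outcome, visit and denominator are settled only after the pattern of missingness is visible, the criterion can be met or missed by the choice.

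**Working it through.** **Inputs.** 60 randomised, 30 per group (sections 3.0, 10.0 and 12.0). Retention benchmark 80% (section 1.0) or 90% (section 12.0). Missing-data limit below 10% (section 1.0) or at most 10% (section 12.0).

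**Step 1: reproduce the plan's figure.** The Wald interval is p ± 1.96 × √(p(1 − p)/60). For p = 0.90 this is 0.90 ± 1.96 × √(0.90 × 0.10/60) = 0.90 ± 0.076, or 82.4% to 97.6%, which agrees with the stated 82% to 98%. So the precision statement is built on 90% retention of 60, not on the 80% of section 1.0.

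**Step 2: turn the rules into counts.**
- Retention of 80%: 0.20 × 60 = 12 may be lost.
- Retention of 90%: 0.10 × 60 = 6 may be lost.
- At most 10% missing: 6 of 60.
- Below 10% missing: 5 of 60 (5/60 = 8.3%; 6/60 = 10.0% is not below 10%).

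**Step 3: apply all four to a 3-month outcome that needs participant contact**, assuming those lost are not assessed and nothing else is missing.

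| Retained | Missing | Retention ≥80% (1.0) | Retention 90% (12.0) | Missing <10% (1.0) | Missing ≤10% (12.0) |
|---|---|---|---|---|---|
| 48 | 12 (20.0%) | pass | fail | fail | fail |
| 53 | 7 (11.7%) | pass | fail | fail | fail |
| 54 | 6 (10.0%) | pass | pass | fail | pass |
| 55 | 5 (8.3%) | pass | pass | pass | pass |

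**Step 4: vary the outcome, visit and denominator with 12 lost.**
- 3-month contact outcome: 12/60 = 20.0%.
- Post-intervention contact outcome, all 12 lost after that visit: 0/60 = 0%.
- Pooled over three visits: 12/180 = 6.7% if all are lost after the post-intervention visit, 24/180 = 13.3% if all are lost before it.
- Pooled over the two post-baseline visits: 12/120 = 10.0% or 24/120 = 20.0%.
- Record-based outcome: record values for 6 of the 12 leave 6 missing and meet the at-most-10% limit; 7 are needed for the below-10% limit.

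The same 12 losses therefore pass or fail according to what is counted.

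**Step 5: how likely are the counts where the rules disagree?** Let X be the number retained, binomial with n = 60 and true retention r. The plan does not predict r, so a range is shown. P(X = 54) is P(X ≥ 54) − P(X ≥ 55).

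| r | P(48 ≤ X ≤ 53) | P(X ≥ 54) | P(X ≥ 55) | P(X = 54) |
|---|---|---|---|---|
| 0.80 | 0.546 | 0.031 | 0.012 | 0.019 |
| 0.85 | 0.709 | 0.185 | 0.097 | 0.088 |
| 0.90 | 0.388 | 0.606 | 0.437 | 0.169 |
| 0.95 | 0.030 | 0.970 | 0.921 | 0.049 |

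For true retention between 80% and 90%, the zone where the two retention rules disagree has probability of roughly 0.39 to 0.71 at the values shown.

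**The case against.** Read alone, Data Analysis Aim 2 is arithmetically coherent: 90% retention allows 6 lost and the missing-data ceiling allows 6 missing. That stands. A reader might infer that a single list both relies on an unnamed primary outcome and accepts 80% retention. It does not. The 80% retention figure is in section 1.0, where the missing-data limit covers outcomes generally. The 80% figures in section 12.0 concern an adherence rate and completion of weekly PCL checklists.

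A reader might also infer that the missing-data limit cannot be met at 80% retention, or that every visit-based outcome must then fail. The documents do not support either reading. Record-based outcomes can exist for people who miss study visits, post-intervention data may be complete, assessment is planned after treatment dropout, and retention is not defined as staying in treatment or being assessed. Section 12.0 also says that the missing-data criterion is meant to show integration with routine care and medical records, which leans towards record-based outcomes. It still names none of them.

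Rules of different strictness are not contradictory in themselves, and 55 or more retained with nothing else missing satisfies all of them. That is true, but a decision rule must also give one answer below 55. The two inequalities differ only at 6 missing. With nothing else missing, that is the count at exactly the plan's own 90% retention target.

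Finally, missing data is one of several feasibility criteria, and the plan gives no expected missingness by outcome. How far the outcomes would differ is therefore unknown.

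**Conclusion.** The point holds as a conflict between stated decision rules, together with one rule that has no referent.

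- Retention: 48 to 53 retained of 60 (80.0% to 88.3%) succeeds under section 1.0 and fails under section 12.0. This needs no assumption about outcome collection, only that retained means the same in both places.
- Missing data: over that range, 3-month contact outcomes are 11.7% to 20.0% missing, assuming those lost are not assessed and all 60 form the denominator. Other permissible readings could still pass.
- Inequality: at exactly 54 retained with nothing else missing, section 12.0 passes and section 1.0 fails.

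The probabilities also assume independent losses at a common rate. The finding does not show that the benchmarks are unattainable, or that the whole feasibility verdict rests on this criterion.

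**What to change.** Before missingness is known:

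1. State one retention threshold in section 1.0 and in both places in section 12.0, and define retained (for example, assessed at 3 months, whether or not treatment was completed).
2. Use one missing-data inequality in sections 1.0 and 12.0.
3. Replace the reference to primary outcome data with outcomes and visits that the protocol already lists. One workable set is CAPS-5 and ART adherence at post-intervention and 3 months, and viral load and attendance at 3 months. The sponsor should confirm whether CD4 count and HIV symptom distress are included; Table 2 shows no instrument under the latter name.
4. Take all 60 randomised as the denominator, report by arm, and require each named outcome to meet the limit at each named visit.
5. Say that the missing-data rule governs where it is stricter than the retention rule.

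The cost is wording only, with no change to visits, instruments or sample size. The downside is that some outcomes may be declared not feasible to collect, which is information that the pilot is meant to provide.

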**Assessments and Data Collection Procedures.** The PC (blind to condition) will conduct the initial eligibility (baseline) diagnostic assessments and all study assessments. The CAPS will be audio-taped and study personnel will listen to a randomly selected 20% to ensure reliability of CAPS diagnosis over the course of the study. The PC will administer the battery in the HIV care clinic or remotely by phone to the participant, based on participant preference. All timepoints will be collected on all participants, even if they drop out of treatment. Pilot trials indicate that major assessments take between 1.5 – 2 hours to complete. Individuals will be given \$50 for completing the baseline interview, \$40 for attending the first session, then \$60 for post-intervention assessments and 20-minute exit interview after completion of CPT-L sessions (i.e., post intervention ~6 weeks after study enrollment); and a \$75 gift card for 3 month follow up surveys. Several questionnaires were drawn from the PROMIS common data elements and NIH sponsored repositories to promote data sharing (e.g., PROMIS depression and BRICS Social Determinants of Health). Participants will complete a brief electronic diary on a weekly basis to assess use of resources/additional supports. Research has demonstrated the validity of this approach, including capturing “real-time” data beyond what can be captured with retrospective reports. Surveys (<1 minute each) will be electronically collected once a week for the 6 weeks of the intervention period starting one week after randomization (i.e., 6 electronic survey entries), leading up to the 3-month follow up. With input from the CAB, we have established procedures to auto-send an email or SMS text (participant choice) on a set schedule. SMS text messaging is possible via Twilio, embedded within our REDCap system, which allows participants to complete a survey directly from their phone, without having to access a webpage. Participants will be asked permission for the study team to access electronic medical records to collect CD4 count and viral load at the time of enrollment. As an attending physician in the clinic, Co-I [name] is familiar with these electronic records and will oversee the data pull. CD4 T-cell counts and HIV viral load will be measured as standard clinical practice using standard clinical assays (HIV viral load less than 200 considered virologic suppression). Relevant data from the clinic’s electronic medical record (e.g., CD4 count, no-shows) will be collected at intervals and study completion (i.e., 6 months after participation) to document retention in HIV clinical care using the industry standard of 2 appointments with a provider with prescribing privileges per year, no longer than 6 months apart. PI [name] has planned for adequate staff training and coverage based on experience. The PI will assist in training research staff on consent, diagnostic interview, assessment measures, and medical chart data retrieval (with Co-I [name] and Co-I [name] for service utilization data) and will conduct weekly meetings, quarterly reviews, and booster trainings to ensure standardized procedures. See Table 2 for research instruments.

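### Acceptable protocol adherence is judged by returned PCL questionnaires across participants, and no numeric feasibility benchmark sets a minimum for CPT-L sessions attended or completed

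*Combined protocol and SAP*

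**What the plan says.** Section 1.0 sets Aim 2 as "To assess feasibility of the modified CPT protocol (CPT-L) compared to Lifesteps in 60 PLWH with comorbid PTSD". Its first benchmark is "Achieve a recruitment rate of 4+ patients per month and retention rate of 80% or higher".

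Section 12.0, Data Analysis Aim 2, gives the working criteria:
- **Recruitment:** at least 4 randomised per month.
- **Retention:** "retain 90% of randomized patients throughout the study", as part of "ability to adequately randomize and retain study participants throughout study intervention and follow-up".
- **Missing data:** at most 10% of primary outcome data missing.
- **Protocol adherence:** "Acceptable protocol adherence will be determined by completion of" at least 80% "of assigned weekly PCL checklists across participants".

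On delivery of therapy, the same section says only this: "Intervention feasibility will be monitored through randomization, session attendance and quality assurance data collection on intervention fidelity and supervision". The distribution of clinician-rated engagement and cooperation is to be reported. Neither statement carries a threshold.

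Section 10.0, Assessments and Data Collection Procedures, adds: "All timepoints will be collected on all participants, even if they drop out of treatment".

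Section 3.0 describes CPT-L as 12 sessions of 90 minutes, twice a week for six weeks. It describes the control condition as one Lifesteps session plus standard of care. Table 2 describes the PCL as a 20-item symptom self-report, collected weekly as well as at the three main assessments.

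**The concern.** The adherence rule measures something other than adherence. A returned PCL shows that a participant answered a symptom questionnaire that week. It does not show that the participant attended therapy. Pooling weakens the rule further, because half the denominator comes from people who were asked to attend one session.

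No other numeric benchmark fills the gap. Recruitment is settled at randomisation, missing data concerns assessments, and retention is undefined. If many CPT-L participants stopped therapy, the stated rule could still label protocol adherence acceptable.

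Delivery of a multi-session trauma therapy is a central thing this pilot has to tell the planned R01. Section 16.0 itself calls the population difficult to engage. The effect and variability estimates taken forward would come from an arm in which an unknown share left treatment early, with nothing stated in advance about how much is too much.

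**Working it through.** **The plan's own figures.** With the normal-approximation interval p ± 1.96·√(p(1−p)/n) and n = 60:
- 90% retention: 0.90 ± 0.076, or 82.4% to 97.6% (plan: 82% to 98%).
- 80% adherence: 0.80 ± 0.101, or 69.9% to 90.1% (plan: 70% to 90%).

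Both reproduce. They also show that the plan assesses adherence precision on all 60 participants.

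**PCL rule by arm.** Inputs are 30 per arm and an 80% threshold (Section 12.0). The number of weekly forms per person is not stated. I assume it is the same for everyone, in which case it cancels. If the control arm completes a share c, the pooled rule needs (c + t)/2 ≥ 0.80, so CPT-L completion t may fall to 1.6 − c:
- c = 100%: 60%
- c = 95%: 65%
- c = 90%: 70%

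**CPT-L participants who stop.** Let k of the 30 stop and return no forms, while everyone else returns a share q. The rule is (60 − k)·q/60 ≥ 0.80, so k ≤ 60 − 48/q:

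| Return by others (q) | 60 − 48/q | Stoppers tolerated, of 30 |
|---|---|---|
| 100% | 12.0 | 12 |
| 95% | 9.5 | 9 |
| 90% | 6.7 | 6 |

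If stoppers return half their forms, the limits are 24, 20 and 15. If they return 80%, all 30 could stop and the rule would still be met.

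**Retention.** Two readings are possible:
- Retained means still assessed. Section 10.0 keeps assessing people who leave treatment, so stopping therapy costs nothing.
- Retained means still in treatment. The 90% rule needs 54 of 60 and allows 6 losses. The 80% rule in Section 1.0 needs 48 of 60 and allows 12. If all fell in CPT-L, that is 6/30 = 20% or 12/30 = 40% of the arm.

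**Taken together (assumed scenario).** Suppose 12 of 30 stop CPT-L and return no weekly forms but attend the post-intervention and 3-month assessments, and everyone else returns everything. Then:
- PCL completion is 48/60 = 80%.
- Retention on the still-assessed reading is 60/60.
- Missing data at the main assessments is 0%.

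All three criteria pass, while CPT-L completion is 18/30 = 60% (exact 95% interval 41% to 77%).

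**The case against.** The strongest reply is that discontinuation would not be hidden. Session attendance, fidelity and supervision data are collected. Engagement ratings are reported alongside PCL completion, attrition is listed as a feasibility outcome, and the acceptability survey is given after treatment discontinuation as well as graduation. Descriptive analyses may also be shown by condition. All of this stands, and the point is limited accordingly: the information will exist, but no numeric rule acts on it.

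Four stronger readings are tempting and go beyond the documents:
- A reader might infer that people who leave therapy are counted as retained. The plan says they continue to be assessed but never defines retained. Data Analysis Aim 2 can be read as retention through the intervention. Section 4.0 lists termination by the investigator for not adhering to the protocol, and Section 14.0 allows withdrawal for not following instructions or attending visits. Some non-attenders might therefore count as losses.
- A reader might infer that every benchmark could be met. Benchmark C of Aim 2 looks for high satisfaction in exit interviews, and feasibility also depends on participant flow. Discontinuation could affect both. Neither has a cut-off, so the statement holds only for the numeric benchmarks.
- A reader might infer that stopping therapy removes later PCL forms from the denominator. The term 'assigned' is undefined, but the analysis section schedules the PCL weekly through intervention and follow-up, which points the other way.
- A reader might infer that the intervention would be largely undelivered. Even in the scenario above, 18 of 30 complete it and the others may have received part of it.

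Pooling over arms is the natural reading of the criterion, although it is not stated in those words.

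**Conclusion.** The concern holds in this limited form. The plan determines acceptable protocol adherence by questionnaire return, and none of its numeric benchmarks sets a minimum for CPT-L attendance or completion. The pooled PCL rule tolerates 6 to 12 of 30 CPT-L participants stopping and returning nothing when the others return 90% to 100%, and more if stoppers return some forms. Depending on how retention is defined, it either ignores stopping therapy or tolerates a loss of 20% (90% rule) or 40% (80% rule) of the CPT-L arm.

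These figures assume 30 per arm, an equal number of weekly forms per person, and pooling over arms. They show what the rules permit and do not predict what will happen.

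**What to change.** 1. Judge CPT-L protocol adherence by session attendance, which is already recorded, over all participants randomised to CPT-L. The investigators should set the criterion in advance and say whether it is the proportion of planned sessions attended or the proportion of participants reaching a stated minimum. The existing 80% refers to forms, and the documents give no basis for carrying it over to sessions.
2. Report attendance at the control arm's Lifesteps session separately.
3. Rename weekly PCL completion as a data-completeness measure. Report it by arm, and keep all scheduled weeks in the denominator after a participant stops therapy.
4. Define retained, report retention by arm, and reconcile the 80% in Section 1.0 with the 90% in Section 12.0.
5. Reconcile the planned session count that the attendance criterion will use. The Section 3.0 text gives 12 sessions, while Table 1 lists a Lifesteps session plus CPT sessions 1 to 12 and an entry of 12+, with variable length as a delivery option.

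This is a change of wording in the aims and analysis sections and needs no new data. The cost is precision and a possibly harder target. A criterion on the proportion of participants would rest on 30 people: 1.96·√(0.8·0.2/30) = 0.143, about ±14 points at 80%, against about ±10 points with 60.
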